## 4.0 Introduction

The Statistical Analysis Plan (SAP) Version 1.0 was written and finalized prior to database lock of the first cohort. Version 2.1 of the SAP was revised and finalized prior to the database lock of Cohort 2.

This statistical analysis plan (SAP) describes the methods to be used during the reporting and analyses of data collected under SPYRYX Biosciences Protocol SPX-101-CF-201.

This SAP should be read in conjunction with the study protocol and CRF. For Cohort 1, Version 1.0 of the plan was developed using the protocol dated 14Nov2017 and CRF dated 11MAY2017. For Cohort 2, Version 2.1 of the plan was developed using the protocol dated 14May2018 and CRF dated 17Jul2018. Any further changes to the protocol or CRF may necessitate updates to the SAP.

### 4.1 Changes from Protocol

Cohort 1 was analyzed per Version 1 of this SAP which covered Protocol Versions 1.0, 2.0 and 3.0).

Version 2 of this SAP covers changes associated with Protocol Version 4.0. The primary changes associated with Protocol Version 4.0 are summarized in Section 6.0.

Protocol Version 4.0 lists “Incidence of antidrug antibodies (ADA)” as an exploratory variable, but this version of the SAP will not include this as an exploratory variable. Instead, ADA will be explored as a safety variable and presented as such.

## 5.0 Study Objectives

### 5.1 Primary Objective

- To evaluate the efficacy of SPX-101 in subjects with Cystic Fibrosis (CF)

### 5.2 Safety Objective

- To evaluate the safety and tolerability of SPX-101 in subjects with CF

### 5.3 Pharmacokinetic Objective

- To assess the extent of systemic exposure to SPX-101 in a subset of subjects

## 6.0 Study Design

This randomized, double-blind, placebo-controlled, Phase II study is designed to evaluate the efficacy and safety of SPX-101 inhalation solution in a 28-day treatment period in approximately 90 adults with CF. Two sequential cohorts were planned to compare the study drug SPX-101 (2 groups) with placebo (1 group) in Cohort 1 (1:1:1 ratio). Cohort 2 compares the study drug SPX-101 (120 mg BID) to placebo in a 2:1 randomization ratio. Each cohort will have its own baseline and will be analyzed separately. To achieve balance between treatment groups, randomization will be stratified by baseline lung function (percent predicted forced expiratory volume in 1 second [ppFEV1] 40.0% to 55.0% or 55.1% to 80.0%) in Cohort 1 and stratified by concomitant hypertonic saline use in Cohort 2.

Cohort 1 treatment groups were the following:

- Placebo twice daily (BID) x 28 days
- SPX-101 60 mg BID x 28 days
- SPX-101 120 mg BID x 28 days

Cohort 2 SPX-101 daily doses were anticipated to not exceed those studied in Cohort 1 and may have included 240 mg once daily (QD), 120 mg QD, 60 mg QD, or 30 mg BID. The actual dose regimens used in the 2 active treatment groups in Cohort 2 were determined by the Sponsor in consultation with the Data Safety Monitoring Board (DSMB) based on the efficacy and safety results of Cohort 1.

Cohort 2 treatment groups are the following:

- Placebo twice daily (BID) x 28 days
- SPX-101 120 mg BID x 28 days

For each cohort, there will be 5 clinic visits and 2 telephone calls: Visit 1 (Screening; Day -28 to Day -3); Visit 2 (Randomization; Day 1); Visit 3 (Day 8 -1); Visit 4 (Day 15 -2/+1); telephone call (Day 22 ± 3); Visit 5 (Day 29 ± 2; end-of-treatment); and a follow-up telephone call 2 days later (Day 31 ± 1; end-of-study). All study visits for an individual subject will be scheduled at approximately the same time of day to minimize the confounding effects of diurnal variation in lung function, background therapies, and daily chest physiotherapy regimens. Subjects will be screened at Visit 1 and then will enter a variable-length screening period of 3 to 28 days to time

Sponsor: SPYRYX Biosciences

Protocol no: SPX-101-CF-201

[figure not shown]
---

the randomization so that the first dose of the investigational product will coincide, if applicable, to the first day ( $\pm 3$  days) of an inhaled antibiotic cycle. If subjects still meet the randomization criteria on Day 1 (Visit 2), they will be randomized to the treatment groups as described. At Visits 2, 3, and 4, after completing spirometry and other assessments, subjects will self-administer the study medication in the clinic. On Day 1 (Visit 2) only, subjects will be monitored for safety for the first 4 hours after completion of administration of the study drug. Monitoring will include spirometry, vital signs, and adverse event (AE) assessments as described in more detail in the protocol. After the 4-hour post dose assessments are complete, subjects who have tolerated the study medication will be discharged with a sufficient supply of medication to take BID on an outpatient basis, until their next clinic visit.

The duration of the study from first subject first visit to last subject last visit will be dependent on the ability of the sites to identify and enroll eligible subjects.

Figures 1 and 2 show the design for Cohort 1 and Cohort 2, respectively. Table 1 shows the schedule of events and assessments.

[figure not shown]
**Figure 1** Study Diagram – Cohort 1

Sponsor: SPYRYX Biosciences

Protocol no: SPX-101-CF-201

**Figure 2      Study Diagram – Cohort 2**

**Table 1 Schedule of Events**

| Visit
(Day)   | Screening        | Treatment Period |            |                |              |                | FU           |
|--|------------------|------------------|------------|----------------|--------------|----------------|--------------|
|  | 1
(-28 to -3) | 2
(1)         | 3
(8-1) | 4
(15-2/+1) | TC
(22±3) | 5
(29±2/ET) | TC
(31±1) |
| Informed consent   | X                |                  |            |                |              |                |              |
| Eligibility  | X                |                  |            |                |              |                |              |
| Randomization a   |                  | X                |            |                |              |                |              |
| Medical history and prior medications                              | X                |                  |            |                |              |                |              |
| Concomitant medications  | X                | X                | X          | X              | X            | X              | X            |
| Vital signs b   | X                | X                | X          | X              |              | X              |              |
| Weight, height c , BMI                                  | X                | X                |            |                |              | X              |              |
| Physical examination d                                  | X                | X                | X          | X              |              | X              |              |
| AE assessment  |                  | X                | X          | X              | X            | X              | X            |
| Spirometry e  | X                | X                | X          | X              |              | X              |              |
| 12-lead ECG  | X                | X                |            |                |              | X              |              |
| CFQ-R  |                  | X                |            |                |              | X f |              |
| Hematology and serum chemistry including electrolytes g | X                | X                |            |                |              | X              |              |
| ADA  |                  |                  |            |                |              | X              |              |
| Urinalysis   |                  | X                |            |                |              | X              |              |
| Urine and blood electrolytes                                       |                  |                  | X          | X              |              | X              |              |
| Pregnancy testing h                                     | X                | X                |            |                |              | X              |              |
| Issue study nebulizer  |                  | X                |            |                |              |                |              |
| IP administration in clinic  |                  | X                | X          | X              |              |                |              |
| 4-hr postdose monitoring i                              |                  | X                |            |                |              |                |              |
| Dispense IP  |                  | X                | X          | X              |              |                |              |
| Cohort 1 only: Plasma PK j                              |                  | X                |            |                |              |                |              |
| Collect unused IP  |                  |                  | X          | X              |              | X              |              |
| Collect study nebulizer  |                  |                  |            |                |              | X              |              |

ADA = antidrug antibodies; AE = adverse event; BMI = body mass index; CFQ-R = cystic fibrosis questionnaire revised; ECG = electrocardiogram; ET = early termination; FU = follow up; IP = investigational product; PK = pharmacokinetics; TC = telephone call

aOnly subjects who meet the randomization criteria at Visit 2 will be randomized (see [Section 9.4.3 of the protocol](#)).

bVital signs will include systolic and diastolic blood pressure, temperature, and heart rate.

Sponsor: SPYRYX Biosciences

Protocol no: SPX-101-CF-201

c Height will be measured only at the screening visit.

d At Visit 1, a full physical examination of all body systems will be performed. At subsequent visits, an abbreviated physical examination (head, ears, eyes, nose, and throat; neck, respiratory, cardiovascular, and skin) may be performed.

e At Visit 2, spirometry including forced expiratory volume in 1 second (FEV1), percent predicted FEV1, forced vital capacity (FVC) and percent predicted FVC will be evaluated pre-dose, and postdose at 30 minutes, 2 hours, and 4 hours. At all other visits, only pre-dose spirometry will be performed.

f The CFQ-R will not be performed for subjects who are terminated early from the study.

g See [Section 11.8 of the protocol](#) for specific laboratory tests to be performed.

h At Screening (Visit 1), a serum pregnancy test will be performed; at Visits 2 and 5, a urine pregnancy test will be performed.

i At Visit 2 only, the subject will be observed and monitored for at least 4 hours after completion of administration of the study drug. The subject may be discharged after 4 hours at the discretion of the Investigator ([See Section 10.2 of the protocol](#)).

j For Cohort 1 only, at Visit 2, blood samples for PK testing will be collected pre-dose and at 5±2 minutes and 15±5 minutes after completion of administration of the study drug.

Note: A subject may be re-screened once if they fail to meet randomization criteria for any reason. If this is the case, a new consent form must be signed and a new screening number will be used.

## 6.1 Sample Size Considerations

In Cohort 1, the study was planned for a minimum of 39 subjects per cohort to be enrolled. The subjects will be randomized in a 1:1:1 ratio to one of the two treatment groups or placebo. The sample size of 39 subjects provided 70% power for the Analysis of Variance (ANOVA) to detect a difference range of 4.5% to 6% in the change from baseline in ppFEV1 and FEV1 between the 2 treatment groups versus placebo, with the two-sided alpha level of 0.15 assuming a common standard deviation of 7%. The attrition rate is expected to be minimal given the 4 week treatment duration.

In Cohort 2, a total of 45 subjects will be randomized in a 2:1 ratio to SPX-101 120 mg BID or placebo. The sample size of 45 subjects will provide 88% to 97% power to detect a difference range of 6% to 8% in the change from baseline in ppFEV1 between the treatment group versus placebo, with the 1-sided alpha level of 0.1 assuming a common standard deviation of 7.58%. The estimated treatment difference and standard deviation are based on the Cohort 1 results from the 120 mg SPX-101 dose group and placebo, among subjects with baseline ppFEV1 between 50.0% and 80.0%, since this reflects the subjects enrolled in Cohort 2.

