**NUMBER OF SUBJECTS:**

In Cohort 1, 46 subjects were randomized in a 1:1:1 ratio to 1 of the 2 treatment groups or placebo. The sample size of 39 subjects was chosen to provide 70% power for the Analysis of Variance (ANOVA) to detect a difference range of 4.5% to 6% in the change from baseline in ppFEV1 and FEV1 between each of the 2 treatment groups versus placebo, with the alpha level of 0.15 assuming a common standard deviation of 7%. The attrition rate was expected to be minimal given the 4 weeks' treatment duration.

In Cohort 2, a total of 45 subjects will be randomized in a 2:1 ratio to either SPX-101 120 mg BID or placebo BID. The sample size of 45 subjects will provide 88% to 97% power to detect a difference range of 6% to 8% in the change from baseline in ppFEV1 between the treatment group versus placebo, with the 1-sided alpha level of 0.1 assuming a common standard deviation of 7.58%.

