### 11.3 Pulmonary Function Tests

Spirometry will be performed at all clinic visits using equipment provided by the centralized spirometry vendor, Biomedical Systems (BMS). Spirometry will be performed in accordance with ATS/ERS guidelines and the GLI predictors of spirometric lung volume normal ranges [2; 3]. At Visit 2, spirometry will be performed pre-dose, and postdose at 30 minutes, 2 hours, and 4 hours postdose after completion of administration of the study drug. At all other visits, only pre-dose spirometry will be performed. The following parameters will be recorded:

- Absolute FEV1 and ppFEV1
- Absolute FVC and ppFVC

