### Change from Baseline

Change from baseline (CFB) will be calculated as (value at post-baseline visit – value at baseline). CFB will be calculated for subjects with both a baseline and post-baseline value as applicable. Percent CFB will be calculated as (CFB/baseline)\*100, where applicable. If a baseline or post-baseline value has not been recorded for a parameter, then CFB will not be calculated for that parameter. Subjects with missing CFB values will be excluded from analyses in which CFB is the endpoint unless otherwise noted.

### Study Day 1

The first day of study product administered.

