#### **12.6.2 Secondary Variables**

##### FEV1

Similar ANCOVA analyses as the primary analysis, using a two-sided significance level of 0.05, will be repeated for testing treatment differences from placebo in the endpoints:

- Change from baseline in FEV1 at visit 3 (week 1)
- Change from baseline in FEV1 visit 4 (week 2)
- Change from baseline in FEV1 visit 5 (week 4)

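### The Cohort 1 sizing sentence credits FEV1 with the 70% power that fits only ppFEV1 at two-sided 0.15; power for FEV1 as the current SAP tests it is not established

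*SAP*

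**What the plan says.** The Cohort 1 sizing sentence stands in three places: the Protocol Synopsis (Number of Subjects), Protocol 13.2 and SAP 6.1. SAP 6.1 reads "The sample size of 39 subjects provided 70% power for the Analysis of Variance (ANOVA) to detect a difference range of 4.5% to 6" percent, and names both spirometry endpoints: "4.5% to 6% in the change from baseline in ppFEV 1 and FEV 1 between the 2 treatment groups versus placebo". The Synopsis differs slightly: "4.5% to 6% in the change from baseline in ppFEV 1 and FEV 1 between each of the 2 treatment groups versus placebo". The error rate and spread in SAP 6.1 are given as "with the two-sided alpha level of 0.15 assuming a common standard deviation of 7" percent. The protocol has the same 0.15 and 7% but does not state sidedness.

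The analysis sections treat the two endpoints differently:

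- **ppFEV1 at Week 4 (primary).** SAP 12.6.1 judges Cohort 1 success at a two-sided 0.15 level.
- **FEV1 (secondary).** SAP 12.6.2 says: "Similar ANCOVA analyses as the primary analysis, using a two-sided significance level of 0.05, will be repeated for testing treatment differences from placebo". This matches the 0.05 default in SAP 12.0.
- **Scale.** Protocol 11.3 records "Absolute FEV 1 and ppFEV 1" as separate parameters. SAP 8.0 says: "Change from baseline (CFB) will be calculated as (value at post-baseline visit – value at baseline". It also defines a percent change for use where applicable, but SAP 12.6.2 lists only change from baseline in FEV1.

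The Cohort 2 sizing sentence names ppFEV1 alone.

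**The concern.** One power figure is attached to two endpoints that the current SAP tests at different significance levels and on different scales. The difference of 4.5% to 6% and the SD of 7% suit ppFEV1, whose change is itself in percent-predicted units. They do not describe a change in absolute FEV1, for which the documents give no SD and no target difference.

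What is at stake is interpretation. Protocol 13.6.4.2 uses FEV1 to check the robustness of the ppFEV1 result. Anyone relying on the sizing text could read a non-significant Cohort 1 FEV1 comparison as a 70%-powered failure to corroborate ppFEV1. On the sizing inputs at 39 subjects and alpha 0.05, a miss has probability 1 − 0.358 = 64% at a true difference of 4.5 and 1 − 0.566 = 43% at 6.

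**Working it through.** **Inputs (SAP 6.1).** N = 39, "randomized in a 1:1:1 ratio to one of the two treatment groups or placebo", so n = 13 per arm; SD 7; differences from placebo 4.5 and 6. Alpha is 0.15 (SAP 6.1 and 12.6.1) or 0.05 (SAP 12.6.2), both two-sided.

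**Step 1: reproduce the printed 70%.** Take a one-way ANOVA with means 0, 4.5 and 6 (grand mean 3.5).

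- Sum of squared deviations: 3.5² + 1.0² + 2.5² = 12.25 + 1.00 + 6.25 = 19.5.
- Noncentrality: λ = 13 × 19.5 / 7² = 253.5 / 49 = 5.17, with 2 and 36 df.
- At alpha 0.15 the critical F is 2.00 and power is **69.8%**. The printed 70% is reproduced.

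The dose-versus-placebo t contrasts at 0.15 (36 df) give 57.1% at 4.5 and 76.3% at 6, so neither gives 70%. The printed figure therefore behaves as an overall F test with both differences present. The documents do not say this outright.

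**Step 2: change only alpha to 0.05.** This borrows the percent-scale difference and SD for FEV1.

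- Overall F: λ is still 5.17 and the critical F is 3.26; power is **48.3%**.
- Each dose against placebo: δ = d / (7 × √(2/13)) = d / 2.746, with 36 df and critical t 2.028. For d = 4.5, δ = 1.64 and power is **35.8%**. For d = 6, δ = 2.19 and power is **56.6%**.

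SAP 12.6.1 and 12.6.2 compare treatment with placebo, so the per-dose range is closer to the written test than the overall figure.

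**Step 3: other Cohort 1 counts, alpha 0.05, SD 7.**

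| Count | Overall F | d = 4.5 | d = 6 |
|---|---|---|---|
| 39 planned minimum (13 per arm) | 48.3% | 35.8% | 56.6% |
| 40 completers (equal split assumed) | 49.4% | 36.6% | 57.8% |
| 45 treated (14/15/16) | 53.9% | 39.4% | 62.9% |
| 46 randomized (equal split assumed) | 56.0% | 41.3% | 64.1% |

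The 40, 45 and 46 come from Protocol 7.3.2 and 13.2. The 14/15/16 split is inferred from the adverse event percentages in Protocol Table 1: 10/14 = 71.4%, 10/15 = 66.7%, 12/16 = 75.0%.

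**Step 4: sensitivity to the SD.** The overall F test at 0.05 with 13 per arm has 61.9% power at SD 6 and 38.3% at SD 8. At SD 7, about 21 per arm would be needed for 70%.

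**Step 5: the scale actually specified.** For FEV1 as value minus baseline, δ needs a difference and an SD in volume units. Neither is given, so no power can be calculated. Steps 2 to 4 are conditional illustrations and are not the power of that test.

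**The case against.** Several points on the other side stand.

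- The 70% is not a miscalculation. It reproduces under the alpha and SD in its own sentence. What is wrong is the reach of the sentence.
- A reader might infer that FEV1 power is 48% at best. It is not a ceiling. It is the overall F figure at the planned minimum of 39; the per-dose figure reaches 57%, and 64% with the 46 randomized. Covariate adjustment in the ANCOVA could raise power further, by an amount the documents do not give.
- A reader might also take 36% to 57% as the power of the specified FEV1 test. The scale mismatch rules that out. If FEV1 were analysed as a percent change, for which SAP 8.0 leaves room, the scale objection would fall away and the alpha mismatch would remain.
- SAP 4.1 says Cohort 1 was analysed under Version 1, which is not supplied. Whether Version 1 tested FEV1 at 0.05 cannot be seen, and Protocol 13.6.4.2 gives FEV1 no alpha. The documents therefore do not support a statement about how the Cohort 1 FEV1 analysis was actually run.
- Cohort 1 is complete and locked, its sizing text is now a record of the design, and no document makes FEV1 a success criterion. Misreading of a null FEV1 result is a possibility, not something shown.

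These points limit the size of the concern. They do not rescue the FEV1 part of the sizing sentence, because Version 2.1 itself still carries the joint 70% claim alongside an FEV1 test at 0.05.

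**Conclusion.** The point holds as an inconsistency within the current text. The 70% belongs to ppFEV1, as an overall ANOVA at two-sided 0.15, and the FEV1 test in SAP 12.6.2 does not have it. On borrowed percent-scale inputs, every Cohort 1 count considered leaves FEV1 below 70% at SD 7: 36% to 57% per dose at 39 subjects, 41% to 64% at 46. On the absolute scale, FEV1 power is not established.

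This rests on reading the 0.05 level from Version 2.1 and on the F-test reading of the printed figure. A reader might infer that Cohort 1 was underpowered for its primary endpoint or wrongly sized. This point does not show that: primary ppFEV1 power, sample size and conduct are untouched. The matter is minor and concerns documentation and reporting.

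**What to change.** Limit the Cohort 1 power statement to ppFEV1 at two-sided 0.15 by removing the reference to FEV1 in the Protocol Synopsis, Protocol 13.2 and SAP 6.1. Since Cohort 1 is locked, a note in the SAP and study report would serve equally well and would leave the recorded design rationale intact: the 70% refers to ppFEV1 only, and no power was established for FEV1. The study report should not describe the FEV1 analysis as 70% powered.

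Do not substitute a new FEV1 power figure as though it applied to the absolute-change test, because the inputs for one are not in the documents. The Cohort 2 sentence needs no change on this point.

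The cost is wording in three places or one note. No data, sample size or analysis changes; the only loss is a stated power for a secondary endpoint.

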## 6.2 Randomization

The Investigator or designee will use an Interactive Voice/Web Response System to randomize eligible subjects for each cohort. In Cohort 1, randomization was stratified by the Visit 2 pre-dose ppFEV1 (between 40.0% and 55.0% vs between 55.1% and 80.0%). Only those subjects who met the randomization criteria were eligible for assignment to study treatment. Subjects who failed to meet the randomization criteria could have had Visit 2 repeated once, or they were considered screen failures. In Cohort 2, randomization was stratified by concomitant use of hypertonic saline. NOTE: The Cohort 2 FEV1 entrance criterion was modified to require a screening ppFEV1 between 50 – 80% of predicted normal thus no stratification by baseline ppFEV1 was undertaken.

# 7.0 Study Variables and Covariates

## 7.1 Primary Efficacy Variables

- Change from baseline in ppFEV1 at visit 5 (week 4)

